2.1 HYPOTHESIS

INO-4800 delivered ID followed immediately by EP will be well-tolerated, exhibit an acceptable safety profile, result in generation of cellular and humoral immune responses

INO-4800	COVID19-311
Inovio Pharmaceuticals, Inc.	Clinical Protocol

to SARS-CoV-2 Spike glycoprotein and provide protection against virologically-confirmed COVID-19 disease in subjects at high risk of SARS-CoV-2 exposure.

3.0 CLINICAL TRIAL DESIGN AND ENDPOINTS

This is an operationally seamless Phase 2/3, randomized, placebo-controlled, multicenter trial to evaluate the safety, immunogenicity, and efficacy of INO-4800, administered by ID injection followed immediately by EP using the CELLECTRA[®] 2000 device, in a 2-dose regimen (Days 0 and 28) in adults who are at high risk of SARS-CoV-2 exposure. Subjects 18 years of age and older are expected to be enrolled across two (2) segments of this study. In the Phase 2 segment, approximately 400 seronegative subjects will be enrolled. In the Phase 3 segment, approximately 6714 seronegative subjects are expected to be enrolled, and 402 seropositive subjects will be enrolled. The subjects and data from Phase 2 are independent from that of Phase 3. The primary objectives of this trial are to identify in seronegative subjects an optimal age-related dose (Phase 2 segment) for subsequent evaluation for efficacy (Phase 3 segment).

Phase 2 Segment – Dose Selection

In the Phase 2 segment, approximately 400 subjects 18 years of age and older will be evaluated across four (4) dose groups (Table 1, Figure 1). Subjects will be randomized at a 3:3:1:1 ratio to receive either 1.0 mg or 2.0 mg of active investigational product (INO-4800) or 1 or 2 injections of placebo (SSC-0001). Dose groups receiving INO-4800 will enroll approximately 150 subjects per group. Dose groups receiving placebo will enroll approximately 50 subjects per group. Randomization will be such that approximately 240 subjects aged 18-50 years, 120 subjects aged 51-64 years and 40 subjects aged \geq 65 years will be enrolled. Initial enrollment will include subjects aged 18-50 years. Initiation of enrollment of older subjects 51-64 years of age and elderly subjects 65 years and older will depend on review of safety and immunogenicity data from those age groups generated in the Phase 1 study (COVID19-001).

Dose selection for evaluation of efficacy in the Phase 3 segment will be based on Week 6 immunogenicity data and Week 8 safety data from the Phase 2 segment. Group-level unblinded summaries and analyses of safety will be produced once the Week 8 phone call visit data are completed for all subjects in the Phase 2 segment. Group-level unblinded summaries and analyses of immunogenicity will be produced once the Week 6 visit data are completed for all subjects in the Phase 2 segment.

Phase 3 Segment – Efficacy

In the Phase 3 segment, approximately 6714 seronegative and 402 seropositive subjects 18 years of age and older will be randomized at a 2:1 ratio to receive either active investigational product (INO-4800, 2.0mg) or placebo (SSC-0001). Approximately half of seronegative subjects and approximately half of seropositive subjects will be 18-50 years of age, and the other half will be \geq 51 years of age as is operationally feasible. Also, approximately 711 subjects will be \geq 65 years of age, if operationally feasible.

Subjects will be randomized in a stratified manner according to (a) age category (18-50 years vs. ≥51 years) on Day 0, and (b) presence of or absence on Day 0 of any of the following underlying medical conditions that increase risk of severe COVID-19 disease, per CDC criteria [1], as listed below:

- Cancer
- Chronic kidney disease

INO-4800	COVID19-311
Inovio Pharmaceuticals, Inc.	Clinical Protocol

- Chronic lung diseases, including Chronic obstructive pulmonary disease (COPD), asthma (moderate-to-severe), interstitial lung disease, cystic fibrosis, pulmonary hypertension
- Neurologic conditions including stroke or cerebrovascular disease, that do not impact cognition
- Diabetes (type 1 or type 2)
- Hypertension
- Heart conditions, such as heart failure, coronary artery disease, or cardiomyopathies
- HIV infection (CD4 count >200 cells/mm3 or undetectable viral load)
- Liver disease
- Obesity (BMI ≥ 30 kg/m2)
- Sickle cell disease or thalassemia, or
- Smoking (current or former smoker).

This segment of the trial is case-driven. Among seronegative subjects, a total of 149 observed cases will be required for 90% power to declare the vaccine efficacious (>30%), assuming a true efficacy of 60%. A sample size of 6714 seronegative subjects is expected to be required to achieve the 149 cases assuming an underlying attack rate of 3.7%. The actual sample size may differ if the observed attack rate is different than projected. There are two formal interim analyses of efficacy; one when 50% of the cases accrue and one when 75% of the cases accrue. If the prespecified criteria for efficacy are met at either interim analysis, then enrollment will continue until 4500 subjects have been enrolled, and blinded follow-up will continue until at least those 4500 subjects have a minimum of 6 months of safety follow-up. At that point, the trial would be unblinded and placeborecipients will be offered the active product.

The primary efficacy endpoint window will begin 14 days post-dose 2 and will end at 12 months post-dose 2. All Phase 3 segment subjects will be followed for 56 weeks from the Day 0 dosing [i.e., Week 56 will be the planned End of Study (EOS) visit for this segment of the trial].

External Committee Reviews

For both the Phase 2 and 3 segments, the Data Safety Monitoring Board (DSMB) will convene regularly to review all available unblinded safety data, and additionally upon completion of the Week 8 phone call visit for all subjects enrolled during the Phase 2 segment. For the Phase 3 segment, the DSMB will also review efficacy in an unblinded fashion. Additionally, for Phase 3, an independent, blinded Endpoint Adjudication Committee (EAC) will review and confirm COVID-19 cases.

Details of each committee's scope will be provided in the respective charters.

3.1 **PRIMARY OBJECTIVES**

See Table 6.

3.2 **PRIMARY ENDPOINTS**

Table 6: Primary Objectives and Associated Endpoints

Phase 2 Primary Objective	Phase 2 Primary Endpoints
 Evaluate the cellular and humoral immune response to INO-4800 administered by ID injection followed immediately by EP 	 1a. Antigen-specific cellular immune response measured by IFN-gamma ELISpot assay 1b. Neutralizing antibody response measured by a pseudovirus-based neutralization assay
Phase 3 Primary Objective	Phase 3 Associated Primary Endpoint
1. Evaluate the efficacy of INO-4800 in the prevention of COVID-19 disease in subjects who are SARS-CoV-2 negative at baseline	 Incidence of virologically-confirmed COVID-19 disease starting 14 days after completion of the 2-dose regimen until 12 months post-dose 2 (End of Study (EOS)) in subjects who are SARS- CoV-2 seronegative at baseline

3.3 SECONDARY OBJECTIVES

See Table 7.

3.4 SECONDARY ENDPOINTS

Table 7: Secondary Objectives and Associated Endpoints

Phase 2 Secondary Objectives Phase 2 Secondary Endpoints	
 Evaluate the safety and tolerability of INO-4800 administered by ID injection followed immediately by EP 	 1a. Incidence of solicited and unsolicited injection site reactions 1b. Incidence of solicited and unsolicited systemic adverse events (AEs) by system organ class (SOC), preferred term (PT), severity and relationship to investigational product 1c. Incidence of serious adverse events (SAEs) 1d. Incidence of adverse events of special interest (AESIs)
Phase 3 Secondary Objectives	Phase 3 Secondary Endpoints
1. Evaluate the safety and tolerability of INO-4800	 1a. Incidence of solicited and unsolicited injection site reactions 1b. Incidence of solicited and unsolicited systemic adverse events (AEs) by system organ class (SOC), preferred term (PT), severity and relationship to investigational product 1c. Incidence of serious adverse events (SAEs) 1d. Incidence of adverse events of special interest (AESIs) 1e. Incidence of all-cause mortality
2. Evaluate efficacy of INO-4800 in the prevention of COVID-19 disease according to degrees of disease severity in subjects who are SARS- CoV-2 seronegative at baseline	 2a. Incidence of non-severe COVID-19 disease in SARS-CoV-2 seronegative subjects starting 14 days after completion of the 2-dose regimen until EOS 2b. Incidence of severe COVID-19 disease in SARS- CoV-2 seronegative subjects starting 14 days after completion of the 2-dose regimen until EOS

		2c. Incidence of deaths due to COVID-19 in SARS- CoV-2 seronegative subjects starting 14 days after completion of the 2-dose regimen until EOS
3.	Evaluate the cellular and humoral immune response to INO-4800	3a. Antigen-specific cellular immune response measured by IFN-gamma ELISpot
		3b. Neutralizing antibody response measured by a pseudovirus-based neutralization assay
4.	Evaluate the efficacy of INO-4800 in the prevention of COVID-19 disease in subjects who are SARS- CoV-2 seropositive at baseline	 Incidence of virologically-confirmed COVID-19 disease starting 14 days after completion of the 2-dose regimen until 12 months post-dose 2 (End of Study (EOS)) in subjects who are SARS- CoV-2 seropositive at baseline

3.5 **EXPLORATORY OBJECTIVE**

See Table 8.

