b. Full physical examination only at Screening and Day 393 (or EOS). Targeted physical exam at other indicated visits.

INO-4800 Inovio Pharmaceuticals, Inc.

- c. In women of childbearing potential. Urine pregnancy test at all indicated visits.
- d. Intradermal injection(s) in skin preferably over deltoid region, or alternately over anterolateral quadriceps region, followed by EP at Day 0 and Day 28.
- e. Following administration of INO-4800 or placebo, a subset of sites will be required to download EP data from the CELLECTRA® 2000 device and provided to Inovio.
- f. AEs to be collected from time of consent to Day 56; SAEs, MAAEs, and AESIs to be collected from time of consent to EOS.
- g. On Day 0, cellular sampling requires 64 mL of whole blood prior to 1st dose. At all other time points, collect 32 mL of whole blood. Cellular samples will be collected at selected clinical sites (estimated to include 711 subjects)
- h. On Day 0, humoral sampling requires a total of 17 mL of whole blood (two 10-mL red top serum collection tubes, each 8.5 mL of whole blood, to produce four serum aliquots of 2 mL each). At all other time points, collect 8.5 mL of whole blood in a single 10-mL red top serum collection tube to produce two serum aliquots of 2 mL each.
- i. SARS-CoV-2 antibody. Screening samples will be tested in the clinic via rapid test to detect antibodies against the Spike protein. Samples collected pre-dose Day 0 and at subsequent timepoints will be tested at a study-designated lab to detect antibodies against the Nucleocapsid protein.
- j. The Day 0 RT-PCR results will not be required prior to dosing on that day.
- k. Day 42 visit must occur at least 10 days after Day 28 visit.
- I. Subjects will be evaluated during a "COVID-19 assessment visit" when acute COVID-19 is suspected. The assessment visit may be performed in the clinic, subject's vehicle, or at a home visit and should be completed within 3 days of symptom onset or within 3 days of a positive result of a SARS-CoV-2 test.
- m. For subjects with virologically-confirmed SARS-CoV-2 infection during the trial, a convalescent visit should be scheduled approximately 28 days after symptom onset, or in the absence of symptoms, after the collection date of any specimen testing positive for SARS-CoV-2 RT-PCR. If acute symptoms are ongoing the site should follow up with the subject via phone call or unscheduled visit after symptom resolution or stabilization

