This segment of the trial is case-driven. Among subjects who are seronegative and RT-PCR negative at baseline, a total of 17 observed severe cases will be required for 90% power to declare the vaccine efficacious (>30%), assuming a true efficacy of 90%. A sample size of 10,002 seronegative subjects is expected to be required to achieve the 17 severe cases assuming an underlying attack rate of 0.4%. The actual sample size may differ if the observed attack rate is different than projected. If the criteria for efficacy are met, placebo-recipients will be offered the active product.

The primary efficacy endpoint window will begin 14 days post-dose 2 and will end at 12 months post-dose 2. All Phase 3 segment subjects will be followed for 56 weeks from the Day 0 dosing [i.e., Week 56 will be the planned End of Study (EOS) visit for this segment of the trial].

External Committee Reviews

INO-4800	COVID19-311
Inovio Pharmaceuticals, Inc.	Clinical Protocol

For both the Phase 2 and 3 segments, the Data Safety Monitoring Board (DSMB) will convene regularly to review all available unblinded safety data, and additionally upon completion of the Week 8 phone call visit for all subjects enrolled during the Phase 2 segment. For the Phase 3 segment, the DSMB will also review efficacy in an unblinded fashion. Additionally, for Phase 3, an independent, blinded Endpoint Adjudication Committee (EAC) will review and confirm COVID-19 cases.

Details of each committee's scope will be provided in the respective charters.

3.1 **PRIMARY OBJECTIVES**

See Table 6.

3.2 **PRIMARY ENDPOINTS**

Table 6: Primary Objectives and Associated Endpoints

Phase 2 Primary Objective	Phase 2 Primary Endpoints
 Evaluate the cellular and humoral immune response to INO-4800 	1a. Antigen-specific cellular immune response measured by IFN-gamma ELISpot assay
administered by ID injection followed immediately by EP	1b. Neutralizing antibody response measured by a pseudovirus-based neutralization assay
Phase 3 Primary Objective	Phase 3 Associated Primary Endpoint
 Evaluate the efficacy of INO-4800 in the prevention of severe COVID-19 disease in subjects who are SARS- CoV-2 seronegative and RT-PCR negative at baseline 	 Incidence of virologically-confirmed severe COVID-19 disease starting 14 days after completion of the 2-dose regimen until 12 months post-dose 2 (End of Study (EOS)) in subjects who are SARS-CoV-2 seronegative and RT-PCR negative at baseline

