3.4 SECONDARY ENDPOINTS

Table 7: Secondary Objectives and Associated Endpoints

Phase 2 Secondary Objectives	Phase 2 Secondary Endpoints
1. Evaluate the safety and tolerability of INO-4800 administered by ID	 Incidence of solicited and unsolicited injection site reactions
injection followed immediately by EP	1b. Incidence of solicited and unsolicited systemic adverse events (AEs) by system organ class (SOC), preferred term (PT), severity and relationship to investigational product
	1c. Incidence of serious adverse events (SAEs)
	1d. Incidence of adverse events of special interest (AESIs)
Phase 3 Secondary Objectives	Phase 3 Secondary Endpoints
1. Evaluate the safety and tolerability of INO-4800	1a. Incidence of solicited and unsolicited injection site reactions
	1b. Incidence of solicited and unsolicited systemic adverse events (AEs) by system organ class

	(SOC), preferred term (PT), severity and relationship to investigational product
	1c. Incidence of serious adverse events (SAEs)
	1d. Incidence of adverse events of special interest (AESIs)
	1e. Incidence of all-cause mortality
2. Evaluate efficacy of INO-4800 in the prevention of COVID-19 disease according to degrees of disease severity in subjects who are SARS- CoV-2 seronegative and RT-PCR negative at baseline	 2a. Incidence of non-severe COVID-19 disease in subjects who are SARS-CoV-2 seronegative and RT-PCR negative at baseline starting 14 days after completion of the 2-dose regimen until EOS 2b. Incidence of COVID-19 disease in subjects who are SARS-CoV-2 seronegative and RT-PCR negative at baseline starting 14 days after completion of the 2-dose regimen until EOS
	2c. Incidence of deaths due to COVID- in subjects who are SARS-CoV-2 seronegative and RT- PCR negative at baseline starting 14 days after completion of the 2-dose regimen until EOS
3. Evaluate the cellular and humoral immune response to INO-4800	3a. Antigen-specific cellular immune response measured by IFN-gamma ELISpot
	3b. Neutralizing antibody response measured by a pseudovirus-based neutralization assay
4. Evaluate the efficacy of INO-4800 in the prevention of COVID-19 disease in subjects who are SARS- CoV-2 seropositive at baseline	 Incidence of virologically-confirmed COVID-19 disease starting 14 days after completion of the 2-dose regimen until 12 months post-dose 2 (End of Study (EOS)) in subjects who are SARS- CoV-2 seropositive at baseline

3.5 **EXPLORATORY OBJECTIVE**

See Table 8.

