6.4.9 COVID-19 DISEASE MONITORING

During both the Phase 2 and Phase 3 segments of the trial, all subjects will be monitored for the development of symptoms suggestive of COVID-19 disease. For the Phase 3 segment, frequent (approximately bi-weekly) scheduled clinic visits or phone calls will occur.

All subjects in the trial should be instructed to do the following:

- Take their temperature daily at home starting on the Day 0 visit for the duration of the trial.
- Monitor for symptoms suggestive of COVID-19 (e.g., feeling feverish or chills, cough, shortness of breath or difficulty breathing, fatigue, muscle or body aches, headache, new loss of taste or smell, sore throat, congestion or runny nose, nausea or vomiting, diarrhea) starting on the Day 0 visit for the duration of the trial.

If at any time during the study, the subject experiences a fever of $\geq 100.4^{\circ}F/38^{\circ}C$ or symptoms suggestive of COVID-19, the subject should contact the site. The site staff should arrange for a clinic visit (COVID-19 assessment visit) within 3 days of the site being aware of either a positive SARS-CoV-2 test or COVID-19 symptom onset. The COVID-19 assessment visit may be performed either at the clinic, in the subject's vehicle or in the subject's home.

Subjects with a confirmed COVID-19 diagnosis, per the case definition outlined in Section 3.7, prior to dose 2 or who have a positive SARS-CoV-2 PCR test at Day 0 will be discontinued from further dosing and will be followed until EOS for safety and resolution of COVID-19. If a subject is due for Dose 2 but SARS-CoV-2 RT-PCR results are not yet available from either Day 0 or a Suspected COVID-19 Assessment Visit, they should be dosed on schedule as long as they are currently asymptomatic.

Subjects with virologically confirmed SARS-CoV-2 infection will return for a convalescent visit approximately 28 days after symptom onset, or in the absence of symptoms, after the collection date of any specimen testing positive for SARS-CoV-2 RT-PCR. If symptoms are ongoing at 28 days after symptom onset, the site should follow up with the subject via phone call or unscheduled visit after symptom resolution or stabilization. Recovery from COVID-19 disease requires either resolution of clinical symptoms except for loss of taste/smell, or with sequelae that appear to be permanent.

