This methodology is based on the following. Assuming that the number of subjects who are cases in the INO-4800 group follows a Poisson distribution with parameter λ_v and the number of subjects who are cases in the placebo group follows a Poisson distribution with parameter λ_c , then conditional on total number of subjects with cases, t, the number of subjects who are cases in the INO-4800 group follows a binomial distribution with parameters (t, $p = \lambda_v/(\lambda_v + \lambda_c)$). The relationship between p and efficacy is: efficacy = (1-(1+k)p)/(1-p). Therefore, testing efficacy > 30% corresponds to testing p < 0.70/(0.70+k). Similarly, the confidence interval for efficacy is (1-(1+k)UB_p)/(1-UB_p), (1-(1+k)LB_p)/(1-LB_p), where UB and LB are the Clopper-Pearson upper and lower limits for the proportion.

The efficacy time frame is defined by symptoms beginning at any time starting from 14 days after Dose 2 and ending 12 months after Dose 2. Subjects identified as cases that started prior to this time point will be excluded. Subjects with multiple instances meeting the case definition will be counted only once, using the first such instance.

The PP population will be primary for the analysis of efficacy in this trial. Efficacy analysis using the mITT population will also be conducted counting cases from 14 days postdose 1 as a supportive analysis. The ITT population will also be used for a supportive analysis counting cases starting from randomization.

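### Secondary endpoint 4 (efficacy in seropositives) is the only Phase 3 efficacy endpoint in version 7.0 without an RT-PCR-negative baseline condition, so its supportive ITT analysis can count infections already present on Day 0

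*Protocol*

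**What the plan says.** All references are to Protocol version 7.0 unless stated otherwise.

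- **Endpoint 4** (Section 3.4, Table 7; same in the synopsis). The objective is "Evaluate the efficacy of INO-4800 in the prevention of COVID-19 disease in subjects who are SARS- CoV-2 seropositive at baseline". The endpoint runs from 14 days after the "2-dose regimen until 12 months post-dose 2 (End of Study (EOS)) in subjects who are SARS- CoV-2 seropositive at baseline".
- **The other Phase 3 efficacy endpoints.** The primary endpoint (Table 6) is set "in subjects who are SARS- CoV-2 seronegative and RT-PCR negative at baseline". Endpoint 2a is "Incidence of non-severe COVID-19 disease in subjects who are SARS-CoV-2 seronegative and RT-PCR negative at baseline" and endpoint 2b is "Incidence of COVID-19 disease in subjects who are SARS-CoV-2 seronegative and RT-PCR negative at baseline". Endpoint 2c and exploratory endpoints 1 and 2 (Table 8) carry the same condition.
- **Day 0 swab** (Table 4, footnote j; Section 6.4.8). Every Phase 3 subject is swabbed before the first dose, but "The Day 0 RT-PCR results will not be required prior to dosing on that day".
- **Dose 2** (Section 6.4.9). A subject with a positive Day 0 RT-PCR gets no further dose. If the result is still outstanding when Dose 2 is due, "they should be dosed on schedule as long as they are currently asymptomatic".
- **Analysis.** Section 8.5.2.1 analyses secondary efficacy endpoints in the primary manner, without a p-value. Under Section 8.5.1 the per-protocol analysis leads and mITT counts cases from 14 days after Dose 1. For ITT, "The ITT population will also be used for a supportive analysis counting cases starting from randomization". Cases are dated by symptom onset, and subjects whose case began before the window are excluded.
- **Missing data** (Section 8.5.8). In ITT, subjects whose case status is missing or unevaluable count as cases.

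**The concern.** A vaccine cannot prevent an infection that is already present at randomization. Such infections fall on the two arms in proportion to their size, so counting them adds the same risk to both and moves the rate ratio toward 1. The RT-PCR condition removes them for the seronegative endpoints. Endpoint 4 has no such protection, so its supportive results follow a different rule from the seronegative ones and are not directly comparable with them. Few events are likely among 402 subjects, so even a handful of baseline infections could shift the point estimate noticeably.

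**Working it through.** **1. Who can enter.** The Day 0 result does not gate dosing, so a seropositive, RT-PCR-positive subject can be randomized and dosed. Such a subject normally gets no Dose 2 and leaves the per-protocol population, which requires all doses (Section 8.4), but stays in mITT and ITT. The case definition (Section 3.7.1) needs a positive RT-PCR and any one listed symptom.

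**2. Which window catches a Day 0 infection.** Section 1.2 gives an incubation period of 2 to 14 days. The latest first onset for an infection acquired by Day 0 is therefore 0 + 14 = Day 14.

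| Analysis | Window opens | Onset by Day 14 |
|---|---|---|
| ITT | Day 0 | inside the window |
| mITT | Day 14 | only the boundary day |
| Per-protocol (as defined in Table 7) | 28 + 14 = about Day 42 | before the window |

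The only other route into mITT is prolonged RT-PCR positivity with a new symptom after Day 14. In the per-protocol analysis the subject must also have received Dose 2 while the result was pending, and the new symptom must come after about Day 42.

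**3. Illustration for ITT.** The protocol states no figure for this, so there is none to reproduce. Arm sizes are from Table 2: 268 INO-4800 and 134 placebo. Three inputs are assumptions:

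- true efficacy v = 60%, the version 6.0 design value;
- attack rate a = 3.7%, the version 6.0 value for seronegatives, with 1% as a lower alternative;
- q, the share of seropositives infected on Day 0 with onset after randomization, which the protocol does not give.

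Apparent efficacy = 1 − [q + (1−q)·a·(1−v)] / [q + (1−q)·a].

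For q = 1% and a = 3.7%:

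- vaccine cases: 268 × (0.01 + 0.99 × 0.037 × 0.4) = 6.61
- placebo cases: 134 × (0.01 + 0.99 × 0.037) = 6.25
- apparent efficacy: 1 − (6.61/268)/(6.25/134) = 47%

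| q (subjects of 402) | a = 3.7% | a = 1% |
|---|---|---|
| 0 | 60% | 60% |
| 0.25% (1) | 56% | 48% |
| 0.5% (2) | 53% | 40% |
| 1% (4) | 47% | 30% |
| 2% (8) | 39% | 20% |

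**4. Effect of the missing-data rule.** Without baseline infections the expected cases at a = 3.7% are 268 × 0.037 × 0.4 = 3.97 and 134 × 0.037 = 4.96. Assume that 5% of subjects have missing case data, about 20, split 2:1. The counts become 3.97 + 13.4 = 17.37 and 4.96 + 6.7 = 11.66, and efficacy is 1 − 0.5 × 17.37/11.66 = 26% before any baseline infection is counted. Four baseline infections, also split 2:1, then lower it to 23%.

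| Assumed missing | No baseline infections | Four baseline infections |
|---|---|---|
| 2% | 39% | 33% |
| 5% | 26% | 23% |
| 10% | 16% | 15% |

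The more data are missing, the less the baseline infections add.

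**The case against.** The strongest defence is that the omission may be deliberate. All the other efficacy endpoints concern seronegatives, where RT-PCR negativity completes an infection-naive definition. Endpoint 4 studies people who have already been infected. This stands to the extent that the text does not prove an oversight. It does not remove the problem: the question is whether vaccination prevents a new episode, and one already under way on Day 0 does not bear on that. The protocol gives no reason for the difference.

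It can also be said that few such subjects will exist. Section 1.2.1 says that antibodies appear in most infected people 10 to 15 days after symptom onset, so many who are both seropositive and RT-PCR positive had their onset before randomization. Fever or acute respiratory symptoms within 72 hours before Day 0 dosing exclude a subject, and the adjudication committee may filter some cases. These points make the number small, but no stated criterion makes it zero.

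Three stronger readings are tempting, and the documents do not support them:

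- **That mITT and per-protocol are similarly contaminated.** Their windows open at Day 14 and about Day 42, at or beyond the stated incubation limit.
- **That post-dose reactions push efficacy below zero.** Tiredness, muscle aches, headache and nausea are both solicited reactions and case-defining symptoms, which may help a Day 0 positive qualify under ITT. But solicited reactions are collected for only 7 days after each dose, so those after Dose 1 precede the mITT window. Nothing in the protocol establishes that INO-4800 causes more of these symptoms than placebo given with the same electroporation.
- **That version 6.0 has the same inconsistency.** There, no efficacy endpoint carries the RT-PCR condition. The discrepancy arose when version 7.0 added it elsewhere.

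**Conclusion.** The point holds as a minor inconsistency in the current endpoint text, with a real but narrow consequence. Under the stated rules, seropositive subjects infected on Day 0 whose symptoms start after randomization can be cases in the supportive ITT analysis of endpoint 4, and this biases that estimate toward zero. The conclusion rests on reading Section 8.5.2.1 as carrying the supportive analyses over to secondary endpoints, and on the protocol's 2 to 14 day incubation range.

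No size can be stated as a finding. The prevalence is not given, the attack rate and efficacy are borrowed from a superseded seronegative design, and the missing-data rule would dilute the shift. The estimate is imprecise in any case: about 9 cases split 4 to 5 give an exact 95% interval for efficacy of roughly −86% to 92%. Endpoint 4 has no hypothesis test, and the primary analysis is unaffected.

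**What to change.** In Table 7, the synopsis and Section 8, define objective and endpoint 4 in subjects who are SARS-CoV-2 seropositive and RT-PCR negative at baseline. Apply this to its supportive ITT and mITT analyses, as for the seronegative endpoints, and list seropositive subjects who were RT-PCR positive on Day 0 separately. If the omission is intended, say so and give the reason.

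The cost is a few words and no new data, since the Day 0 swab is already scheduled for every Phase 3 subject. The few subjects who were RT-PCR positive on Day 0 leave the seropositive efficacy set.
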